#### 3.5.2. Laboratory Data

Safety laboratory tests will be performed as described in the protocol.

The investigator must review the laboratory report, document this review, and record any clinically significant changes occurring during the study in the AE section of the CRF. Clinically significant abnormal laboratory test findings are those that are not associated with the underlying disease, unless judged by the investigator to be more severe than expected for the participant's condition.

Baseline will be the last predose measurement in each study period.

To determine if there are any clinically significant laboratory abnormalities, the hematological, clinical chemistry (serum) and urinalysis safety tests will be assessed against the criteria specified in the sponsor reporting standards. The assessment will take into account whether each participant's baseline test result is within or outside the laboratory reference range for the particular laboratory parameter.

## 3.5.3. Vital Signs

Single assessment supine blood pressure and pulse rate measurements will be taken at screening, day 1 at hour 0, follow-up visit and at early termination (if applicable). Triplicate supine measurements will be taken at all other times as detailed in the Schedule of Activities given in the protocol. The average of the triplicate measurements will be calculated prior to analyzing the data. Respiratory rate will be measured as a single assessment at each timepoint specified in the protocol.

Baseline for these measures will be defined as the last predose measurement in each study period.

The following endpoints will be determined:

- Change from baseline (CFB) in systolic and diastolic BP, pulse rate and respiratory rate
- The minimum and maximum post-dose systolic and diastolic BP, pulse rate and respiratory rate
- The maximum increase and decrease from baseline over all measurements taken postdose for systolic and diastolic BP, pulse rate and respiratory rate values

The maximum decrease and increase from baseline over all measurements taken post-dose will be calculated for supine systolic and diastolic blood pressures and pulse rates. The maximum increase from baseline will be calculated by selecting the maximum change from baseline over the respective period, except in the case where a participant does not show an increase. In such an instance, the minimum decrease should be taken. Similarly, the maximum decrease from baseline will be determined by selecting the minimum value of the change from baseline. In cases where a participant does not show a decrease, the minimum increase should be taken.

### 3.5.4. Electrocardiograms

A single 12-lead ECG will be obtained on all participants at screening, follow-up visit and at early termination (if applicable). 12-lead ECGs will be recorded in triplicate at all other times as detailed in the Schedule of Activities given in the protocol. The average of the triplicate readings collected at each assessment time will be calculated for each ECG parameter.

The average of the triplicate ECG measurements over the 3 pre-dose measurement times (-1H, -0.5H, and predose 0H; total of 9 ECG measurements) collected before morning dose administration on Day 1 will serve as each participant's baseline value in each study period.

ECG endpoints include heart rate, QT interval, PR interval and QTcF and QRS complex. If not supplied QTcF will be derived using Fridericia's heart rate correction formula:

QTcF = QT / 
$$(RR)^{1/3}$$
 where  $RR = 60/HR$  (if RR not provided).

The following endpoints will be determined:

- Change from baseline in QT, QTcF, PR, QRS interval and heart rate
- The maximum post-dose QTcF, heart rate, PR and QRS interval
- The maximum increase from baseline over all measurements taken post-dose for QTcF, heart rate, PR and QRS values

The maximum increase from baseline will be calculated by selecting the maximum change from baseline over the respective period, except in the case where a participant does not show an increase. In such an instance, the minimum decrease should be taken.

### 3.5.5. Continuous Cardiac Monitoring

Continuous cardiac monitoring will be performed using telemetry as outlined in the protocol.

All abnormal rhythms will be recorded and reviewed by the study physician for the presence of rhythms of potential clinical concern. The time, duration, and description of the clinically significant event will be recorded in the CRF. Events deemed of clinical concern will be recorded as AEs and will be summarized as part of the standard AE outputs.

### 3.5.6. Physical Exam

Complete physical exam will be carried out at screening or upon admission for a participants first period in the study; at all other timepoints a brief physical exam may be performed for the findings during a previous exam or new/open AEs at the investigators discretion. Height and weight will only be measured at the screening visit.

Physical examination findings collected during the study will be considered source data and will not be required to be reported, unless otherwise noted. Any untoward physical examination findings that are identified during the active collection period will be captured as AEs or SAEs, if those findings meet the definition of an AE or SAE.

### 4. ANALYSIS SETS (POPULATIONS FOR ANALYSIS)

Data for all participants will be assessed to determine if participants meet the criteria for inclusion in each analysis population prior to unblinding and releasing the database and classifications will be documented per standard operating procedures.

Table 3. Analysis Sets

Participant Analysis Set	Description	Applicable Analysis (for additional information refer to section 6)
Enrolled	"Enrolled" means a participant's agreement to participate in a clinical study following completion of the informed consent process and randomization to study intervention. A participant will be considered enrolled if the informed consent is not withdrawn prior to participating in any study activity after screening. Potential participants who are screened for the purpose of determining eligibility for the study, but do not participate in the study, are not considered enrolled, unless otherwise specified by the protocol.	
Safety analysis set	All participants randomly assigned to study intervention and who take at least 1 dose of study intervention. Participants will be analyzed according to the study intervention they actually received.	Section 6.6 Safety Summaries and Analyses
PK Concentration Set	All participants randomly assigned to study intervention and who receive at least 1 dose of study intervention and in whom at least 1 plasma concentration value is reported.	Section 6.3.1 PK Endpoints
PK Parameter Set	All participants randomly assigned to study intervention and who receive at least 1 dose of study intervention and have at least 1 of the PK parameters of interest calculated.	Section 6.3.1 PK Endpoints
CCI		

### 5. GENERAL METHODOLOGY AND CONVENTIONS

### 5.1. Hypotheses and Decision Rules

There are no formal statistical hypotheses or decision rules in this study.

#### 5.2. General Methods

Unless otherwise stated, all summaries and plots will be presented by treatment. If a dose level is repeated across 2 or more cohorts, the data will be combined, unless the dose is in a different food state (e.g. after an MMTT), in which case the dose would be reported separately.

Unless otherwise stated the summary tables and/or statistical analyses will only include a single pooled placebo group across all included cohorts. Placebo will be pooled from all dose escalation periods but not the fed period.

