Lunch and dinner will be standardized when participants are confined in the CRU; additional efforts will be made to ensure lunch, dinner and snacks are as identical as is feasible on Day 1 for each period and on Day -1 where time-matched assessment is performed (Section 5.3.2).

CCI

Based on predicted half-life in human (~4 hours), PK samples were collected over 48 hours post-dose in Cohort 1. However, the preliminary PK data emerging from Cohort 1 suggested the terminal half-life could be longer than the predicted 4 hours therefore, participants in remaining Cohort 2 and optional Cohort 3 will be confined in CRU up to Day 4 with PK samples collected up to 72 hours post-dose. A washout interval of ≥ 7 days is proposed between doses within an individual participant; this interval should be sufficient based on all emergent PK data to date, and the projections that CCI levels return to baseline within approximately 72 hours post-dose based on a PK/PD model developed with preclinical data and emergent PK/PD data in Cohort 1. In addition, this washout interval should offer sufficient opportunity to review safety, tolerability, and PK data after each dosing period prior required for decision on the PF-07328948 dose to be evaluated in the subsequent period. However, sampling times, duration of sampling, and/or the length of the washout period may be modified and/or extended based on emerging PK and/or PD data. Participants may be asked to remain at the CRU after completion of Day 4 activities at the discretion of the investigator or if safety, tolerability, or PK data dictate the need to prolong inpatient stay in the CRU. The planned doses and assignment to study intervention in the escalation sequence (see Section 1.2) may be modified or repeated, as guided by emerging safety, tolerability, and PK data but will follow the dose-escalation rules defined in Section 6.6.1.

Decreased blood pressure was observed after single doses (≥ 20 mg/kg) of PF-07328948 in dogs in exploratory toxicology studies; however, no significant blood pressure changes were subsequently noted in GLP toxicology studies after single doses of ≤ 100 mg/kg in dogs. Serial triplicate assessment of blood pressure will be performed following single dose administration as outlined in SoA. Triplicate 12-lead ECGs and continuous cardiac telemetry

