#### 3.3. Other Endpoint(s)

#### 3.3.1. PK Endpoints

Blood samples for PK analysis of PF-07328948 will be taken according to the Schedule of Activities given in the protocol.

The plasma PK parameters for PF-07328948, following oral dose administration, will be derived from the plasma concentration-time profiles using standard noncompartmental

methods as detailed in Table 2, as data permit. Table 2 shows the analysis scale and method for each parameter.

In all cases, actual PK sampling times will be used in the derivation of PK parameters. In the case that actual PK sampling times are not available, nominal PK sampling time will be used in the derivation of PK parameters.

Table 2. Plasma PF-07328948 PK Parameters

Parameter	Definition	Method of Determination	Analysis Scale	PF-07328948
AUClast	Area under the plasma concentration-time curve from time 0 to the time of the C last	Linear/Log trapezoidal method	ln	D,A
AUCinf*	Area under the plasma concentration-time curve from time 0 extrapolated to infinite time	AUClast + (Clast*/kel), where Clast* is the predicted plasma concentration at the last quantifiable timepoint estimated from the log-linear regression analysis	ln	D,A
Стах	Maximum plasma concentration	Observed directly from data	ln	D,A
Tmax	Time for Cmax	Observed directly from data as time of first occurrence	R	D
t ½ *	Terminal elimination half-life	Loge(2)/kel, where kel is the terminal phase rate constant calculated by a linear regression of the log-linear concentration-time curve. Only those data points judged to describe the terminal log-linear decline will be used in the regression.	R	D
CL/F*	Apparent clearance	Dose/AUCinf	ln	D
Vz/F*	Apparent volume of distribution	Dose/(AUC inf k el )	ln	D
AUClast(dn)	Dose-normalized AUClast	AUClast/Dose	ln	D
AUCinf(dn)*	Dose-normalized AUCinf	AUCinf/Dose	ln	D
Cmax(dn)	Dose-normalized Cmax	Cmax/Dose	ln	D

[figure not shown]
Key: D=displayed with descriptive statistics,

ln=natural-log transformed, R=raw (untransformed),

A=analysed using a statistical model (for specific treatment groups for evaluating food effect)

 $T_{last}$  will also be provided as a support parameter for AUClast.  $T_{last}$  values will only be listed and not summarized.

\*=if data permits, dn = normalized to a 1mg PF-07321332 dose

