#### **6.3. Other Endpoints**

#### 6.3.1. PK Endpoints

 $t_{1/2}$ 

The PK parameters detailed in Section 3.3.1 will be listed and summarized for participants in the PK Parameter Analysis Set (as defined in Section 4). Missing values will be handled as detailed in Section 5.3. Each PK parameter will be summarized by dose (and fasting condition, if appropriate) as applicable. Each summary will include the set of summary statistics as specified in Table 4.

Parameter	Summary Statistics
AUC last , AUC inf , C max , CL/F,	N, arithmetic mean, median, cv%, standard deviation,
$V_z/F$ , $AUC_{last}(dn)$ ,	minimum, maximum, geometric mean and geometric
$AUC_{inf}(dn), C_{max}(dn)$	cv%.
T	N median minimum mayimum

arithmetic mean, median,

standard

deviation.

Table 4. PK Parameters to be Summarized Descriptively

The plasma PK parameters will be summarized descriptively by dose (and fasting condition, if appropriate) as applicable. Dose-normalized AUCinf, AUClast, and Cmax will be plotted against dose (and fasting condition, if appropriate) using a logarithmic scale, and will include individual participant values and the geometric means for each dose. These plots will be used to understand the relationship between the PK parameters and dose (and fasting condition, if appropriate).

minimum, maximum.

Geometric means will have a different symbol than the individual values. A footnote will be added to the plots to indicate that geometric means are presented. All dose normalized parameters will be listed along with other individual PK parameters.

Supporting data from the estimation of  $t_{1/2}$  will be listed by treatment and dose where applicable: terminal phase rate constant ( $k_{el}$ ); goodness of fit statistic from the log-linear regression ( $r^2$ ); the percent of AUCinf based on extrapolation (AUCextrap%); and the first, last, and number of time points used in the estimation of  $k_{el}$ . These data may be included in the CSR.

Presentations for PF-07328948 concentrations will be presented using participants in the PK Concentration Set (as defined in Section 4) and will include:

- a listing of all concentrations sorted by participant ID, dose and nominal time post-dose. The concentration listing will also include the actual times. Deviations from the nominal time will be given in a separate listing.

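### Minor: if drug is quantifiable after 48 h, AUClast covers 0-48 h in Cohort 1 but up to 72 h later, and the AUClast(dn)-versus-dose plot has no common-window companion or schedule marker

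*SAP*

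**What the plan says.** Protocol 4.2 gives two sampling windows. "PK samples were collected over 48 hours post-dose in Cohort 1", whereas Cohort 2 and optional Cohort 3 have "PK samples collected up to 72 hours post-dose". The reason given is that early Cohort 1 data suggested "the terminal half-life could be longer than the predicted 4 hours". Protocol 4.1 agrees: discharge was on Day 3 in Cohort 1 and is on Day 4 afterwards.

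SAP Table 2 (section 3.3.1) defines AUClast as "Area under the plasma concentration-time curve from time 0 to the time of the" last quantifiable concentration. Tlast is supplied as a supporting parameter, but its "values will only be listed and not summarized".

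SAP 6.3.1 plots dose-normalised AUCinf, AUClast and Cmax "against dose (and fasting condition, if appropriate) using a logarithmic scale, and will include individual participant values and the geometric means for each dose". On their purpose it says: "These plots will be used to understand the relationship between the PK parameters and dose".

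For pooling, SAP 5.2 says: "If a dose level is repeated across 2 or more cohorts, the data will be combined, unless the dose is in a different food state". Food state is the only exception; sampling schedule is not mentioned.

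The visible Tables 2 and 4 contain no AUC over a fixed interval, and SAP 2.1 records no modifications. AUClast is a secondary endpoint and AUClast(dn) is exploratory (SAP 2.2).

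**The concern.** AUClast is comparable between cohorts only if the time of the last quantifiable sample is not set by the schedule. Sampling was extended to 72 h because drug appeared to persist longer than predicted, so quantifiable drug after 48 h is a realistic possibility. If it occurs, there are two consequences.

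- **Dose plot.** Cohort 1 doses are integrated to 48 h and later-cohort doses to as much as 72 h, on one axis. Part of any difference in AUClast(dn) then comes from the schedule, always in the direction of larger values in later cohorts. This needs no repeated dose.
- **Pooled summary.** If a Cohort 1 dose is given again later in the same food state, one AUClast summary for that dose mixes the two windows.

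At stake is the reading of a descriptive plot and, possibly, one row of a descriptive table for a secondary endpoint. A reader could take a schedule step for part of the dose-exposure relationship.

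**Working it through.** The plan states no figure for this effect, so there is nothing to reproduce. The size is illustrated under stated assumptions.

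**From the documents:** last sample at 48 h (Cohort 1) or 72 h (later cohorts); predicted half-life about 4 h, with longer suspected but no value given; about 6 active participants per dose level. Current grid (Protocol Tables 1 and 2): 0, 0.5, 1, 1.5, 2, 3, 4, 8, 12, 24, 36, 48, 72 h. For Cohort 1, the amendment summary shows that a 16 h sample was taken and the 72 h sample was not.

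**Assumed:** quantifiable drug to the last sample; the terminal half-lives h below; absorption rate 2/h; a first phase with a 4 h half-life; between-participant CV of 25-40%.

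**Step 1, mono-exponential decline.** Ratio R = (1 − 2^(−72/h)) / (1 − 2^(−48/h)).

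| h (hours) | numerator | denominator | R | √R |
|---|---|---|---|---|
| 4 | 1.0000 | 0.9998 | 1.000 | 1.000 |
| 8 | 0.9980 | 0.9844 | 1.014 | 1.007 |
| 12 | 0.9844 | 0.9375 | 1.050 | 1.025 |
| 18 | 0.9375 | 0.8425 | 1.113 | 1.055 |
| 24 | 0.8750 | 0.7500 | 1.167 | 1.080 |
| 36 | 0.7500 | 0.6031 | 1.243 | 1.115 |
| 48 | 0.6464 | 0.5000 | 1.293 | 1.137 |

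R does not level off at 24 h; it keeps rising with h.

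**Step 2, two phases.** Let a share f of AUC lie in the slow phase. Ignoring absorption, AUC to time T is proportional to (1 − f)(1 − 2^(−T/4)) + f(1 − 2^(−T/h)).

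- f = 0.10, h = 12: 0.9984 / 0.9935 = 1.005.
- f = 0.50, h = 24: 0.9375 / 0.8749 = 1.072.

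Applying the linear/log trapezoidal rule to the two actual grids, with absorption, gives these AUClast ratios (72 h schedule over 48 h schedule):

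| h (hours) | f = 10% | f = 30% | f = 50% |
|---|---|---|---|
| 12 | 1.008 | 1.020 | 1.030 |
| 18 | 1.013 | 1.037 | 1.059 |
| 24 | 1.017 | 1.048 | 1.080 |

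These slightly exceed the closed form, mainly because the later grid lacks the 16 h sample.

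**Step 3, pooled repeat.** With 6 participants from each schedule, the pooled geometric mean exceeds the 48 h value by a factor √R: 1.004-1.039 for the two-phase cases, and 1.025-1.080 for mono-exponential at 12-24 h.

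**Step 4, noise scale.** The standard error of a log geometric mean with n = 6 is √(ln(1 + CV²)/6). This is 0.101, 0.120 and 0.157 for CV of 25%, 30% and 40%, or about 11%, 13% and 17%.

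**Step 5, what a common window achieves.** In the two-phase cases the AUC0-48 ratio between schedules is 1.0025-1.0074, which is the residue of the 16 h change. The AUCinf ratio, with the terminal slope from the last three points, is 1.005-1.033.

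**Step 6, samples below the assay limit before 48 h.** Running the trapezoid down to a zero at the next sample adds (interval × last concentration)/2. In the two-phase cases this adds 0.7-3.9% when the last quantifiable sample is at 36 h and 2.6-7.2% when it is at 24 h. That is similar in size to the artefact, so the convention has to be stated.

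**The case against.** The strongest reply is that little is hidden and little depends on it.

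- AUCinf(dn), which is meant to remove dependence on the last sampling time, is plotted alongside if data permit.
- Tlast and the extrapolated share of AUCinf are listed.
- SAP 6.3.1 also plans individual, mean and median concentration-time plots, and concentration summaries by dose and nominal time with counts above the assay limit. A dose without 72 h data would show there.
- No hypothesis is tested, and Protocol 9.3.2.2 permits further PK analyses.
- In the two-phase cases the effect is below one standard error of a six-person geometric mean.

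All of this stands, and it keeps the point minor. It does not remove it. The listings and profiles reveal the truncation but do not make the plotted or pooled AUClast values comparable. AUCinf is conditional, and a long half-life also leaves more of it to extrapolation: with mono-exponential decline and h = 24 h, 25% is extrapolated after 48 h against 12.5% after 72 h. Unlike sampling noise, the schedule effect has one direction and can be removed.

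A reader might infer that pooled summaries will mix windows. The documents do not show this: the dose-by-cohort schema is not visible, so whether any Cohort 1 dose is repeated in the same food state is unknown.

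**Conclusion.** The point holds as a minor, conditional improvement. It rests on one condition, quantifiable drug after 48 h, which the documents make plausible but do not establish. If the condition fails, the effect is nil. If it holds, the illustrations are about 1-8% for a 12-24 h terminal phase carrying 10-50% of AUC, about 5-17% for mono-exponential decline at 12-24 h, and more for longer half-lives. A reader might take 17%, or 8% for a pooled mean, as a ceiling. Neither is one: both come from stopping the assumed half-life at 24 h.

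A reader might also infer that dose escalation or a formal dose-proportionality result is at risk. The documents do not support that. The stopping limits in Protocol 6.6.1 use Cmax and AUC24, which both schedules cover. No dose-proportionality model is planned, only plots. Cmax is untouched, and the food-effect model uses Cohorts 2 and 3 only.

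The finding is limited to the visible SAP, whose version table is partly redacted.

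**What to change.** Before analysis, amend the SAP as follows.

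- Add AUC0-48 and AUC0-48(dn) to Tables 2 and 4 and to the dose plots as supportive parameters, beside AUClast and AUCinf and not in place of them.
- Mark each point on the AUClast(dn) plot as 48 h or 72 h schedule.
- Footnote any pooled AUClast summary that mixes schedules.
- State a separate noncompartmental convention: when the last quantifiable sample is before the nominal 48 h sample, AUC0-48 is taken as AUClast; otherwise the nominal 48 h sample, at its actual time, closes the window. This should not be presented as following from SAP 5.3.2, which sets values below the assay limit to zero for data presentations and gives no integration rule.
- Record the addition in SAP 2.1.

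The cost is one extra derived parameter with its dose-normalised form, a plot symbol, a footnote and some SAP wording. No new samples are needed. One limit remains: a Cohort 1 profile last quantifiable at 16 h has no matching sample in later cohorts, and AUC0-48 does not correct that.

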Participants confirming eligibility according to Section 5 will be admitted to the CRU on Day -2 in Period 1 for each cohort and the 1st food period (if applicable) within a cohort. For all other periods (ie, Periods 2-4 except the 1st food period within each cohort), participants will be re-admitted to the CRU on Day -1. For each period in this study, on Day 1, following ≥10-hour overnight fast, participants will receive a single oral dose of PF-07328948 or placebo. Participants have been discharged on Day 3 in Cohort 1 and will be discharged on Day 4, following completion of all scheduled assessments out to 72 hours post-dose in Cohort 2 and optional Cohort 3. Participants may stay in the CRU after completion of Day 4 activities at the discretion of the investigator. In each cohort, a washout interval of at least 7 days will be introduced between subsequent doses. During the washout interval, emerging 24-hour PK and 48-hour safety data will be reviewed and the next dose will be determined. An on-site follow-up visit on Day 8±1 after the final dose and a final follow-up within 28-35 days after the final dose will be scheduled. Final follow-up may be a phone contact or an on-site visit at the discretion of the PI.

Based on the review of emerging safety, tolerability, and PK data (and PD data if available) in Cohorts 1 and 2, the optional third cohort may enroll 8 participants (crossover, placebo-controlled design) to explore additional doses, to repeat a dose, to evaluate split dosing, or to investigate food effects on PK and PD biomarkers.

Dosing will occur in the fasted state for all periods for dose escalation. The effect of a high-protein meal on safety, tolerability, PK exposure, and PD biomarkers may be assessed in at least 1 period within Cohort 2 and/or Cohort 3.

Participants should only need to undergo these time-matched assessments of PD biomarkers on Day -1 once in the fasted state and/or once in the fed state in each cohort, unless there is any uncertainty regarding the reliability of the initial Day -1 assessment. In addition, if thought necessary to achieve study objectives, study intervention may be administered in the fed state (eg, following a high-protein meal) during any of the study periods/cohorts.

The total duration of participation from the screening visit to the telephone follow-up contact will be approximately 14 weeks.

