### 5.2.3. Mixed Model for Repeated Measurements (MMRM)

An MMRM model will be used with treatment, time (as a factor), treatment-by-time interaction, baseline and baseline-by-time interaction as fixed effects. Time will be fitted as a repeated effect within each participant\*period. Baseline will be included as two separate variables, the average baseline for the participant, and the deviation of each treatment period baseline from the average baseline for each participant. An unstructured covariance matrix will be fitted to the repeated times within participant (other covariance matrices will be considered if necessary, e.g. if the model does not converge).

The Least Squares (LS) means (and standard errors, 90% confidence intervals and 2-sided p-values) will be obtained for each treatment at each timepoint. Differences (and standard errors, 90% confidence intervals and 2-sided p-values) between LS means will also be obtained, comparing each dose versus placebo. If data have been logged, LS means and differences (including CI's) will be back transformed to give percent changes from baseline ([relative change from baseline -1]\*100), and percent change from placebo ([ratio of relative change from baseline -1]\*100).

Example SAS code is provided in Appendix 2.

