#### 6.6.3. Vital Signs

Absolute values and changes from baseline in supine systolic and diastolic blood pressure, pulse rate and respiratory rate will be summarized by treatment and timepoint, according to sponsor reporting standards, using the safety analysis set defined in Section 4. Baseline is as defined in Section 3.5.3.

Mean changes from baseline for supine systolic and diastolic blood pressure, pulse rate and respiratory rate will be plotted against time post-dose. On each plot there will be one line for each treatment. Dats from all cohorts will be plotted on the same figure using a single line for the placebo group(s). Corresponding individual plots of changes from baseline will also be produced for each treatment.

Maximum increase and decrease from baseline over all measurements taken post-dose for supine systolic and diastolic blood pressures, pulse rate and respiratory rate will be summarized by treatment, according to sponsor reporting standards.

Minimum and/or maximum absolute values and changes from baseline for supine vital signs will also be summarized descriptively by treatment using categories as defined in Appendix 1.

Numbers and percentages of participants meeting the categorical criteria will be provided. All planned and unplanned post-dose time points will be counted in these categorical summaries.

Data collected at screening that are used for inclusion/exclusion criteria, will be considered source data, and will not be required to be reported, unless otherwise noted.

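### If the optional fed period is run, SAP 5.2 gives fed-period placebo no treatment group and displays the fed active dose beside fasted placebo only

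*SAP*

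**What the plan says.** - SAP 5.2 sets the default for placebo: "Unless otherwise stated the summary tables and/or statistical analyses will only include a single pooled placebo group across all included cohorts". It then defines the pool: "Placebo will be pooled from all dose escalation periods but not the fed period".
- The same section combines a dose level repeated across cohorts, "unless the dose is in a different food state (e.g. after an MMTT), in which case the dose would be reported separately". A fed active dose therefore gets its own group.
- Protocol 4.1 fixes the food state of the pool: "Dosing will occur in the fasted state for all periods for dose escalation". It also randomizes every period 3:1, active to placebo.
- Protocol 4.1 makes the fed assessment optional, in Cohort 2 and/or Cohort 3: "The effect of a high-protein meal on safety, tolerability, PK exposure, and PD biomarkers may be assessed in at least 1 period". The schema footnotes give Period 3 of Cohort 2 as an example.
- SAP 6.6.1 to 6.6.4 summarize adverse events, laboratory data, vital signs and ECGs by treatment. None mentions fed placebo. The vital-sign figures carry one placebo line. The plot of QTcF change against concentration places placebo at zero concentration and does not distinguish food state.
- Protocol Table 2 places the meal about 20 minutes before dosing and schedules 12-lead ECG, blood pressure and pulse on Day 1 only.
- SAP 3.5.4 takes the ECG baseline as the average over -1, -0.5 and 0 h. SAP 3.5.3 takes the last predose value for vital signs.

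**The concern.** The SAP separates active treatment by food state but does not do the same for placebo. Keeping fed placebo out of the fasted pool is sound. The gap is that fed placebo is then given nowhere else to appear by treatment. A reader of the ECG or vital-sign tables would see a fed dose next to a placebo column in which nobody had the pre-dose meal. Any effect of that meal on heart rate, blood pressure or QTcF could be taken for an effect of the drug, or could mask one.

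The primary objective is safety, and the protocol says the meal's effect on safety and tolerability may be assessed. In the QTcF-concentration plot, all points at zero concentration would be fasted while the fed active points carry the meal, so a meal shift could look like a concentration effect. No drug-free fed Day -1 profile exists for ECG, blood pressure or pulse to help a reader tell the two apart.

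**Working it through.** **1. The plan's own figures (Protocol 9.5).** 3 cohorts × 8 = 24 participants. Per period, 8 × 3/4 = 6 active and 8 × 1/4 = 2 placebo. Both reproduce.

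**2. Where the placebo doses fall.** This assumes that all 4 periods run in each cohort and that one period is fed.

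| Cohorts run | All placebo doses | Fed placebo | Fasted pool |
|---|---|---|---|
| 2 | 2 × 4 × 2 = 16 | 2 | 14 |
| 3 | 3 × 4 × 2 = 24 | 2 | 22 |

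**3. What the display compares.** Let a be the drug effect and m the meal effect, taken as additive.

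- Fed active minus fasted placebo: a + m.
- Fed active minus fed placebo: a.

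With a = 0 these are m and 0. Sample size does not enter, so more participants would not shrink the first difference.

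**4. How much the period baseline removes.** Let f, between 0 and 1, be the share of m already present at 0 h. Let m be constant afterwards.

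- ECG: with the meal at about -20 min, the -1 and -0.5 h readings precede it. The baseline carries f·m/3, so the change from baseline keeps m(1 − f/3), which lies between 2m/3 and m.
- Blood pressure and pulse: the scheduled baseline is the single 0 h value, so the change keeps m(1 − f), which lies between 0 and m.

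The documents give no meal effect. For assumed values (ms, bpm or mm Hg) and no drug effect:

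| Assumed m | Difference in absolute values | ECG change from baseline, at least | BP or pulse change from baseline |
|---|---|---|---|
| 2 | 2 | 1.3 | 0 to 2 |
| 5 | 5 | 3.3 | 0 to 5 |
| 10 | 10 | 6.7 | 0 to 10 |

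**5. Which time points.** Table 2 has post-dose ECG, blood pressure and pulse on Day 1 at 1, 2, 3, 4, 8 and 12 h. Lunch follows the 4 h samples and dinner comes at about 10 h, in fed and fasted periods alike. The unmatched meal is the pre-dose one, so the mismatch bears mainly on 1 to 4 h.

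**6. Would adding fed placebo to the single pool help?** Hardly. In absolute values the difference would be m − 2m/16 = 0.875m with 14 fasted doses, or m − 2m/24 = 0.917m with 22.

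**7. Precision of a separate fed-placebo group.** SE = SD × √(1/6 + 1/n).

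- n = 2: 0.82 SD.
- n = 14: 0.49 SD.
- n = 22: 0.46 SD.

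This treats doses as independent, which is only approximate in a crossover.

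**The case against.** **No planned analysis is biased.** The strongest reply is that SAP 5.1 has no hypotheses or decision rules, and that the vital-sign and ECG sections specify summaries by treatment, not a fed-dose-minus-placebo difference. This stands. A reader might infer that the SAP will report a meal effect as a drug effect. The documents support only that the display invites that reading.

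**Meal and drug can be separated another way.** If the same dose is also given fasted, fed against fasted active shows the meal, and fasted active against fasted placebo shows the drug. This stands in part, so it would be too strong to say that no safety output can separate the two. However, fed minus fasted active also contains any change in exposure caused by food. The fed dose need not match a fasted one either: SAP 6.3.1 allows dose-normalization in the food-effect analysis.

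**The SAP does not say fed placebo is dropped.** The rule opens with an exception clause, SAP 6.6.3 allows for a plural of placebo group, the safety set covers everyone dosed, and adverse events are also listed and summarized overall. A reader should therefore not conclude that these data are discarded. Even so, no visible section uses the exception, and the rule that outputs "will only include a single pooled placebo group across all included cohorts" leaves fed placebo no group by treatment.

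**The pharmacodynamic model.** SAP 5.2.3 describes contrasts "comparing each dose versus placebo", and a reader might infer that a fed dose is contrasted with fasted placebo there, so that BCAA lowering is understated. The documents do not support this. The pharmacodynamic baseline and endpoints are redacted, the exception clause may be used there, and the protocol plans a time-matched Day -1 biomarker profile in the first fed period. No size can be put on this.

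**Small consequence.** The fed period is optional and fed placebo is about 2 participants. Both are true. They limit the weight of the point without removing it.

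**Conclusion.** The point holds in a limited form. If a fed period is run and SAP 5.2 is followed literally, the fed dose appears beside a placebo group that is entirely fasted (14 doses with two cohorts, 22 with three, given one fed period). About 2 fed placebo participants then have no treatment group in the adverse event, laboratory, vital-sign and ECG outputs.

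The possible misreading equals the meal effect in absolute values. For ECG change from baseline it is at least two thirds of a constant meal effect. For blood pressure and pulse change from baseline it is somewhere between none and all. It concerns chiefly the 1 to 4 h values.

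This rests on an additive meal effect whose size the documents do not give, on a meal time of about 20 minutes before dosing, and on the visible text of SAP 6.6 being complete for safety outputs. It is a defect of descriptive display and affects no planned test or estimate.

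**What to change.** Keep the exclusion of fed placebo from the fasted pool, and add to SAP 5.2 wording along these lines:

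> Placebo given in a fed period is presented as a separate treatment group, placebo fed. Fasted-period placebo remains pooled as placebo fasted. A fed dose is read against placebo fed, and a fasted dose against placebo fasted. With about 2 participants per fed period, placebo fed is descriptive only.

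Carry this through the adverse event, laboratory, vital-sign and ECG tables and plots in SAP 6.6.1 to 6.6.4, including the single placebo line in the vital-sign figures. Give fed placebo its own symbol in the QTcF-concentration plot. For the pharmacodynamic models, state only that any placebo contrast for a fed dose is matched on food state, unless the redacted text already says so.

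The cost is a short SAP edit plus one extra column or line per output, using data already collected and changing no procedure. The price is imprecision: 0.82 SD for the fed comparison against 0.49 SD with the pool of 14, so the new group can give context but cannot settle a small difference.
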